# 6.4 Method for Assigning Subjects to Study Arms

Randomization will be done through the Interactive Web and Voice Response System (IXRS) at any time during the visit. Subjects will be informed about their study arm allocation at the end of V3. Subjects will be randomized in one of the four study arms:

- Cigarette arm with training program
- *IQOS*-1 arm with training program
- SA arm with training program
- *IQOS*-2 arm without training

Data and information contained in this document are considered to constitute trade secrets and confidential commercial information, and the legal protections provided to such trade secrets and confidential information are hereby claimed under the provisions of applicable law. No part of this document may be publicly disclosed without the written consent of Philip Morris Products S.A

Philip Morris Products SA	Clinical Study Protocol	Confidential
P1-EXC-01-EU	Version 3.0 / 2 May 2019	Page 56 of 151

in a 5:5:5:3 ratio using a stratified randomization based on daily cigarette consumption over the 12 months prior to V1 (10-19 cigarettes/day vs. >19 cigarettes/day), and sex. All subjects will be instructed to adhere to their assigned product/regimen until they complete the study.

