To describe changes in biological health markers in subjects switching to *IQOS*, continuing to smoke cigarettes and being smoking abstinent

For each of the biological markers descriptive statistics will be employed to assess the changes from baseline for each arm. An appropriate (linear or non-linear) statistical model may be employed to estimate differences across arms at V14, V28 and V43. Covariates such as age, sex, cigarette consumption and/or *IQOS* use or any other clinically relevant covariates of interest will be adjusted statistically and further defined in the SAP.

Data and information contained in this document are considered to constitute trade secrets and confidential commercial information, and the legal protections provided to such trade secrets and confidential information are hereby claimed under the provisions of applicable law. No part of this document may be publicly disclosed without the written consent of Philip Morris Products S.A

Philip Morris Products SA	Clinical Study Protocol	Confidential
P1-EXC-01-EU	Version 3.0 / 2 May 2019	Page 106 of 151

To describe changes in weight, body fat and waist circumference in subjects switching to *IQOS*, continuing to smoke cigarettes and being smoking abstinent

For weight, body fat and waist circumference, descriptive statistics will be employed to assess the changes for each arm. An appropriate statistical model may be employed to estimate differences across arms at V4 and V43. Covariates such as age, sex, cigarette consumption and/or *IQOS* use or any other clinically relevant covariates of interest will be adjusted statistically and further defined in the SAP.

To monitor levels of exposure to CO, nicotine, nitrosamines and acrylonitrile in subjects switching to *IQOS*, continuing to smoke cigarettes and being smoking abstinent

Descriptive statistics of exhaled CO will be summarized and presented for each arm. An appropriate statistical model may be employed to estimate differences across arms at the end of the study. Covariates such as age, sex, cigarette consumption and/or *IQOS* use or any other clinically relevant covariates of interest will be adjusted statistically and further defined in the SAP. Descriptive statistics of COHb% in blood, NEQ, NNAL and CEMA in urine will be summarized and presented for each arm. An appropriate statistical model may be employed to estimate differences across arms during the visits where these are measured.

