lsmeans ARM / diff=control("IQOS-1") CL alpha=0.05;
```

Confidentiality Statement

Philip Morris Products SA.	Statistical Analysis Plan	Confidential
P1-EXC-01-EU	Final 2.0	Page 46 of 71
Related to PMI-RRP-WKI-112487		SAP_P1-EXC-01-EU
lsmeans MONTH*ARM / diff lsmeans MONTH*ARM / diff	ol("IQOS-2") CL alpha=0.05; =control("MONTH#X" "CC") CL =control("MONTH#X" "IQOS-1") =control("MONTH#X" "IQOS-2")	CL alpha=0.05;

The percentage of time active and percentage of time very active will be summarized on a monthly basis descriptively.

For each subject, average step counts will be plotted at baseline (V2-V3), Months 1 to 3. These will be presented as boxplots with step count on the y-axis and time on the x-axis for each product use group.

In addition, moving averages using a 7-day time window for daily step counts for all subjects will be plotted as well. If data is missing on one or more days, the average step count will be divided by the number of valid days available over the 7 day period. These will be plotted for all subjects versus day and color coded by product use arm. A separate plot will be created by averaging the daily moving average for each subject within a product use arm and plotted against time as well.

9.6.1.1.6 To describe changes in biological health markers in subjects switching to IQOS (with and without training), continuing to smoke cigarettes (with training) and being smoking abstinent (with training)

The SAS procedure PROC MIXED will be used with the restricted maximum likelihood method for evaluation of the biological health markers at V14, V28 and V43. The dependent variable will be the change from baseline of the biological health markers with age, sex, arm, visit, visit*arm, baseline cigarette consumption at V1 and daily cigarette consumption as covariates. Subject will be fitted as a random effect.

The baseline values of the parameters (V3) will be considered as covariate and other clinically relevant covariates of interest may be added as deemed appropriate. Estimates of the endpoints and their 95% confidence intervals within each arm will be reported and also between arms as per Table 5.

An example of SAS code for the model to be used is provided below:

```
proc mixed data= _DATA_ method=reml order=data;
class SUBJECT VISIT ARM SEX CC_CONS_GRP;
model CHANGE = BASELINE ARM SEX AGE CC_CONS_GRP DAILY_CC_USE VISIT
VISIT*ARM /ddfm = kr;
random SUBJECT / subject = SUBJECT;

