lsmeans VISIT*ARM / diff=control("14" "CC") CL alpha=0.05 bylevel e;
lsmeans VISIT*ARM / diff=control("14" "IQOS-1") CL alpha=0.05 bylevel e;
lsmeans VISIT*ARM / diff=control("14" "IQOS-2") CL alpha=0.05 bylevel e;
```

Confidentiality Statement

Philip Morris Products SA.	Statistical Analysis Plan	Confidential
P1-EXC-01-EU	Final 2.0	Page 47 of 71
Related to PMI-RRP-WKI-112487		SAP P1-EXC-01-EU
	diff=control("28" "CC") CL alpha	-
lsmeans VISIT*ARM /	diff=control("28" "IQOS-1") CL a	lpha=0.05 bylevel e;
lsmeans VISIT*ARM /	diff=control("28" "IQOS-2") CL a	lpha=0.05 bylevel e;
lsmeans VISIT*ARM /	diff=control("43" "CC") CL alpha	=0.05 bylevel e;
lsmeans VISIT*ARM /	diff=control("43" "IQOS-1") CL al	lpha=0.05 bylevel e;
lsmeans VISIT*ARM /	diff=control("43" "IQOS-2") CL al	lpha=0.05 bylevel e;
run;		

9.6.1.1.7 To describe changes in weight, body fat and waist circumference in subjects switching to IQOS, continuing to smoke cigarettes and being smoking abstinent

The SAS procedure PROC MIXED as described above for biological health markers will be used to evaluate the change from baseline in body fat and waist circumference (V4 and V43) with age, sex, visit, product use, visit*product use and daily cigarette consumption as covariates. Subject will be fitted as a random effect. Also the baseline values of the parameters (V3) will be considered as covariate and other clinically relevant covariates of interest may be added as deemed appropriate. Estimates within and between groups similar to those shown in Table 4 and Table 5 will be provided.

For body weight, the model presented in section 9.6.1.1.3 will be used to assess the changes at V14, V28 and V43 with change from baseline (V3) as the endpoint and age, sex, visit, product use, visit*product use and daily cigarette consumption as covariates. Subject will be fitted as a random effect. Also the baseline values of the parameters (V3) will be considered as covariate and other clinically relevant covariates of interest may be added as deemed appropriate. Estimates within and between groups at V14, V28 and V43 will be calculated together with their respective 95% confidence intervals.

Box plots for the change from baseline in weight for the study arms by month will be presented. For body fat and waist circumference we will present the study arms side by side separately for each visit (V4 and V43).

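### SAP 9.6.1.1.7 lists covariates for body fat, waist and weight without V1 cigarette consumption, a randomization stratum, while the models it refers to include it

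*SAP*

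**What the plan says.** Protocol 6.4 assigns subjects "using a stratified randomization based on daily cigarette consumption over the 12 months prior to V1" (10-19 or >19 cigarettes per day) and sex.

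SAP 9.6.1.1.7 covers objective 8 with two models, each defined partly by reference and partly by a list:

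- **Body fat and waist (V4, V43).** By reference: "The SAS procedure PROC MIXED as described above for biological health markers will be used", that is, 9.6.1.1.6. By list: change from baseline "with age, sex, visit, product use, visit*product use and daily cigarette consumption as covariates".
- **Body weight.** By reference: "For body weight, the model presented in section 9.6.1.1.3 will be used to assess the changes at V14, V28 and V43". By list: change from V3 "as the endpoint and age, sex, visit, product use, visit*product use and daily cigarette consumption as covariates".

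Both models also take the V3 value as a covariate, fit subject as a random effect and leave room for further covariates at the analyst's discretion. The section has no code of its own.

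The referenced 9.6.1.1.6 names "baseline cigarette consumption at V1 and daily cigarette consumption as covariates", and 9.6.1.1.3 names the same two terms. According to SAP 9.6.1, all these analyses compare groups defined by actual product use in the exercise-compliant set.

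**The concern.** A list that repeats its parent model almost term by term and lacks one term looks like a replacement for the parent's list. The missing term is a stratification factor, and the contrasts are not between randomized arms. Subjects are placed in the cigarette, IQOS, abstinent or dual-use groups by what they report using, so stratified randomization does not guarantee that these groups are balanced on prior smoking. Heavier prior smoking could plausibly influence both the group a subject ends up in and how weight changes afterwards. If so, part of a between-group difference in weight, body fat or waist could reflect prior smoking. The documents themselves give no evidence on either link.

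There is also a reproducibility problem. One programmer could follow the list and another the referenced code. Tables 15.2.2.7.1 to 15.2.2.7.3, 15.2.2.7.5 and 15.2.2.7.6 would then come from different models.

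**Working it through.** No sample size, power or alpha figure bears on this point. The check compares texts.

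**Step 1. Where V1 consumption appears in the SAP models.**

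| SAP section | Endpoint | V1 consumption in text | In code |
|---|---|---|---|
| 9.6.1.1.1 | VO2max | Exploratory candidate; backward selection may drop it | Generic covariate placeholders |
| 9.6.1.1.2 | Exercise capacity | Exploratory candidate, same procedure | No separate code |
| 9.6.1.1.3 | Training intensity | Listed | `CC_CONS_GRP` |
| 9.6.1.1.4 | Blood composition, respiratory; VO2 and heart rate against workload | Listed | `CC_CONS_GRP` (VO2 and heart rate code) |
| 9.6.1.1.5 | Step count | Listed | `CC_CONS_GRP` |
| 9.6.1.1.6 | Biological health markers | Listed | `CC_CONS_GRP` |
| 9.6.1.1.7 | Body fat, waist, weight | Not listed | None; refers to 9.6.1.1.6 and 9.6.1.1.3 |

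**Step 2. Term-by-term comparison with the parents.** The code in 9.6.1.1.6 begins "model CHANGE = BASELINE ARM SEX AGE CC_CONS_GRP DAILY_CC_USE VISIT" and adds the visit-by-arm interaction. Set against it, both lists in 9.6.1.1.7 keep age, sex, visit, group (renamed from arm to product use), the interaction and daily cigarette use, and the section adds the V3 value separately. The only term lost is V1 consumption. The comparison with the text of 9.6.1.1.3 gives the same result.

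**Step 3. Whether the remaining cigarette term covers the gap.** SAP 9.6.1.1.1 describes daily cigarette consumption as self-reported use from randomization to each visit, and 9.6.1.1.7 does not redefine it. It is a post-randomization quantity taken from the same diaries that define the product-use groups (SAP 5.5 and 5.5.1). It is therefore not a baseline adjustment.

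**Step 4. Size.** To first order, the shift in a contrast from leaving the stratum out is

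shift ≈ γ × Δp,

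where γ is the effect of >19 versus 10-19 cigarettes per day on the outcome, given the other covariates in the model, and Δp is the difference between groups in the share of >19/day smokers. The documents give neither input. Purely as an assumed illustration, with γ from 0.5 to 2 outcome units and Δp from 10 to 40 percentage points:

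- low end: 0.5 × 0.10 = 0.05 units
- high end: 2 × 0.40 = 0.8 units

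This range shows how the shift scales. It is not an estimate for this trial.

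**The case against.** The strongest defence is that the adjustment may already be there. Both models are defined by reference to ones that include V1 consumption in text and code, no competing code is given, and further covariates may be added. This stands to the extent that a reader who infers that the objective 8 contrasts are certain to lack the adjustment goes too far. The documents support a conflict between list and referenced model, and no more than that. The discretionary clause does not resolve the conflict. The same clause appears in 9.6.1.1.6 next to an explicit mention of V1 consumption, so it is not how that term enters a model. The blinding in SAP 4.3.2.2 also covers only VO2max and exercise capacity, so a choice left open for weight, fat and waist could be made with outcomes visible by group.

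Three further readings are tempting and not supported:

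- **That the protocol clearly requires this covariate for objective 8.** Protocol 12.5 says: "differences across arms at V4 and V43. Covariates such as age, sex, cigarette consumption". The sentence goes on to pair that term with IQOS use, is illustrative, and leaves the definition to the SAP. It does not say baseline or V1, whereas the VO2max paragraph separates baseline from self-reported consumption. Daily cigarette use could satisfy it.
- **That SAP section 7 should have declared a departure.** This falls with the previous reading.
- **That every other arm-comparison model includes the term.** For VO2max and exercise capacity it is only a candidate that may be eliminated.

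It is also fair to say that little rests on these contrasts. The study tests no hypothesis, objective 8 is descriptive, and the protocol makes modelling of these outcomes optional.

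**Conclusion.** The point holds as a conflict within SAP 9.6.1.1.7. Its two covariate lists omit V1 cigarette consumption, and the two models it invokes contain it. Under the list, contrasts between self-selected product-use groups go unadjusted for a randomization stratum. Under the reference, they are adjusted. The SAP does not say which applies.

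Any bias under the list reading depends on imbalance in prior smoking between groups and on a conditional stratum effect. Neither can be obtained from the documents, so no magnitude is claimed. Because the study is descriptive and no decision rule uses these results, the change is nice to have and not essential.

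**What to change.** In SAP 9.6.1.1.7, add cigarette consumption at V1 (10-19, >19 per day) as a fixed covariate to both lists, the one for body fat and waist and the one for body weight. The lists then agree with 9.6.1.1.3 to 9.6.1.1.6 and with the `CC_CONS_GRP` term in the referenced code. Printing the MODEL statement for each of the two models would remove any remaining doubt. If the omission was deliberate, the section should say so and give the reason.

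The cost is one degree of freedom per model and a few words. The variable is already collected and already used in the other models.

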9.6.1.2 Descriptive Analysis and Listing of Endpoints

Non-safety endpoints will be listed and summarized for the AEECS using the study arm and by visit or by month in the case of more densely collected endpoints. See Section 9.1.2 "Descriptive Statistics" for a summary of continuous and categorical variables.

In general, the descriptive statistics for the endpoints will be grouped by the following arms, Group1: CIGARETTE, IQOS-1, IQOS-2 and SA. Another set of descriptive statistics Group 2: Dual-1, Dual-2 and Others will be also presented to manage the size of the tables.

The endpoints related to the VO2max (including RPC; respiratory parameters; heart rate and oxygen uptake at VO2max) and exercise capacity test will have baselines dependant on the product use group for the Week 1 (acute) and Overall (training) analysis period. These baselines will be distinguished as Acute Baseline and Training Baseline respectively. All other endpoints will have their baseline dependant on the product use Overall.

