1.1 Revision History

Table should only include approved version and needs to be completed starting with version 1, the initial version of the document.

Version	Date of Revision	Revision
1.0	06 Dec 2019	Initial Version
2.0	09 Mar 2020	 Updated wording in formula for calculation of Nicotine Equivalents in 5.1.1. Added IPAQ scoring algorithm in 5.3.5 The calculation of product use categories is simplified to only be done for Week 1 and from V3 – V43 (Overall) or visit before early termination where applicable. For subjects with insufficient product use data they will be classified under the "Other" group per section 5.5.1. The definition of completion of a bike training is expanded to include cases where at least 20 minutes of training was done and also those which were done but without data due to technical issues. Added 9.1.7 to describe how to handle data which is implausible.

Confidentiality Statement

Philip Morris Products SA.

Statistical Analysis Plan Final 2.0 Confidential Page 6 of 71

Related to PMI-RRP-WKI-112487

P1-EXC-01-EU

SAP_P1-EXC-01-EU

Version	Date of Revision	Revision
		 Descriptive statistics for VO2_{max}, exercise capacity and other related endpoints will now include an acute and training baseline that is based on product use categories calculated at Week 1 and Overall, respectively, this is related to third bullet point above. Clarified the analysis in 9.6.1.1.2 for exercise capacity to include or exclude subjects which did not have the correct work load performed. Added a sensitivity analysis to assess the impact when all subjects including those with the wrong workloads are analysed. Removed some boxplots for VO₂max and exercise capacity based on subgroups. Added demographics for AEBECS Added tables for analysis sets and reason for exclusion from analysis sets and number of subjects in each analysis set. Added tables for exercise capacity, biological health markers and biomarkers of exposure for AEBECS. Removed some redundant listings and updated listing numbers. Fixed typos throughout document.

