5.5.1 Product Use Pattern

Actual product use pattern categorization is described in Figure 2 below,

Confidentiality Statement

Figure 2: Product Use Categorization

Note: HS: HeatSticks

The calculation of product use categories will be performed based on Figure 2. For each subject we will calculate product use for two time periods, representing Week 1 use and average product consumption from V3 till end of Month 3 or last visit prior to early termination whichever comes first.

- From V3 to V4: Week 1
- From V3 to V43/Last visit before early termination: Overall average consumption

For each time period the daily product use reported by a subject in the study will be summed up and averaged by the actual number of days the subject was in the study after randomization until date of last reported product use within the respective time period. This will then be multiplied by 30 to describe the average monthly product use.

For subjects who early terminated from the study, product use for overall average consumption will be calculated until the last visit prior to V44. For example, if a subject early terminated at V23 and subsequently came for V44, then product use will be calculated from V3 until the date of V23.

As both electronic diaries and paper diaries were used in the study concurrently for some subjects, the following rules will be applied in case of inconsistencies.

Confidentiality Statement

Philip Morris Products SA.	Statistical Analysis Plan	Confidential
P1-EXC-01-EU	Final 2.0	Page 29 of 71
Related to PMI-RRP-WKI-112487		SAP_P1-EXC-01-EU

- When there is data available for both electronic and paper diaries for the same date, the electronic diary data will be kept if both are the same. If the data is different on the same date, then data for this date will be considered missing.
- If a subject reports no product use but a value is recorded, we will assume that the number of product used reported was correct and use it in the derivation of product use.

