Missing data for self-reported daily use will not be imputed and we will assume that the derived average monthly use from non-missing data is representative of the actual usage. For each analysis period (Week 1 or Overall), if more than 50% of product use data is not available then the subject will be grouped into the 'Others' product use arm. Therefore, it is possible that a subject is not considered for statistical modelling as it is grouped into 'Others' for Week 1 (3 out of 7 days of product use data only) but available for analysis for the entire study period if more than 50% of product use data was eventually collected throughout the study. A subject may have switched product use groups throughout the study and the total number of subjects in an arm may fluctuate over time depending on the actual product use.

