5.5.2 Cigarette Use

The average number of cigarettes used by each subject from familiarization V2 to V3 will be calculated, in addition the average from baseline (V3) to the following visits will be calculated, these visits include V4, V14 (Month 1), V28 (Month 2), V43 (Month 3) which corresponds to cigarettes smoked from baseline to acute effect visit, end of Month 1, end of Month 2 and end of Month 3 respectively.

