9.6.1.2.8 Exposure to CO, nicotine, nitrosamines and acrylonitrile

For exhaled CO and COHb% in blood both the observed values and the changes from baseline will be listed and summarized at Baseline, V4 and by month (see section 9.1.3.1) for each arm. The reporting of COHb% will on the log-scale then back-transformed to obtain the geometric means.

For NEQ, NNAL and CEMA in urine the values adjusted for creatinine will be listed. For the latter also the changes from baseline will be listed. The values adjusted for creatinine and their changes from baseline will be summarized by visit and arm. Similar to COHb%, these values will be log-transformed and means calculated, these values are then back transformed to obtain the geometric means.

Data and information contained in this document are considered to constitute trade secrets and confidential commercial information, and the legal protections provided to such trade secrets and confidential information are hereby claimed under the provisions of applicable law. No part of this document may be publicly disclosed without the written consent of Philip Morris Products S.A

Philip Morris Products SA.	Statistical Analysis Plan	Confidential
P1-EXC-01-EU	Final 2.0	Page 51 of 71
Related to PMI-RRP-WKI-112487		

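### Exposure markers at V4, and exposure and health markers at V14, appear to be grouped by product use that mostly comes after the measurement (at V28, partly); the SAP should name the classification period for each visit

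*SAP*

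**What the plan says.** SAP 5.5.1 fixes the number of classifications: "For each subject we will calculate product use for two time periods". These are Week 1 (V3 to V4) and Overall (V3 to V43, or to the last visit before early termination). The revision history in SAP 1.1 shows this was deliberate: "The calculation of product use categories is simplified to only be done for Week 1" and for V3 to V43.

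SAP 9.6.1.2 assigns the groupings. Endpoints tied to the VO2max test (RPC, respiratory parameters, heart rate and oxygen uptake included) and to the exercise capacity test get an acute baseline by Week 1 group and a training baseline by Overall group. For the remainder: "All other endpoints will have their baseline dependant on the product use Overall". SAP 9.1.3.1 agrees, limiting period-specific baselines to certain endpoints related to VO2max and exercise capacity.

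Several of the remaining endpoints are reported well before V43:
- For exhaled CO and COHb, observed values and "changes from baseline will be listed and summarized at Baseline, V4 and by month" (SAP 9.6.1.2.8). NEQ, NNAL and CEMA are summarised by visit, and Protocol 3.1 places them at V3, V4, V14, V28 and V43.
- A mixed model is planned "for evaluation of the biological health markers at V14, V28 and V43" (SAP 9.6.1.1.6).
- Body fat and waist are modelled at V4 and V43 (SAP 9.6.1.1.7).

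The SAP expects groups to change. It says "A subject may have switched product use groups throughout the study" (SAP 5.5.1), and SAP 9.4 anticipates dual use and relapse.

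**The concern.** Suppose a subject uses only HeatSticks until V28 and then returns to cigarettes. At V4, V14 and V28 the COHb and NNAL values reflect HeatStick use alone. If the Overall average decides the group, those values may be shown under another label because of smoking that had not yet happened. A late switch in the other direction carries early cigarette exposure into a different group.

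The design rationale (Protocol 4.2) is that lower COHb after switching improves exercise capacity. A reader will want to set COHb at one week beside VO2max at one week. VO2max at V4 has a Week 1 grouping; COHb and the other exposure markers appear to follow Overall. The two tables would carry the same arm labels over different subjects.

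**Working it through.** The plan gives no figure on this point to reproduce. The check is which window classifies each visit, and how much of that window lies after the measurement.

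**Step 1: is Overall the grouping for post-baseline values?** The SAP 9.6.1.2 sentence names only the baseline. Three things carry the inference further. Change from baseline is the post-baseline value minus the baseline value (SAP 9.1.3), so a group summary of change needs the same subjects at both times. No V14 or V28 category exists. Week 1 is reserved for the exercise-test endpoints. For descriptive tables, Overall is the only coherent reading at V14 and V28, and the natural one for the V4 exposure markers.

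**Step 2: how much of the window is later?** Visit days after V3: V4 at 7 (SAP 4.1), V14 at 40 and V28 at 68 (Protocol 9.4.2), V43 at 106 (SAP 4.1), each ±2. Share after the visit = (day of V43 − day of visit) / day of V43. Ranges use the extremes of the visit windows.

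| Visit | Calculation | Share after visit | Range |
|---|---|---|---|
| V4 | (106 − 7)/106 = 99/106 | 93% | 91% to 95% |
| V14 | (106 − 40)/106 = 66/106 | 62% | 60% to 65% |
| V28 | (106 − 68)/106 = 38/106 | 36% | 33% to 39% |

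Most of the window is later at V4 and V14. At V28 about 64% is earlier, and even at the extremes of the visit windows the later share stays below half.

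**Step 3: can later use move a subject?** Figure 2 is not shown, so its thresholds are unknown. As an assumption, take the diary limit for abstinence in SAP 8.4, at most 5 cigarettes per month, and ignore that SAP 8.3, read literally, asks for no product use in the SA arm. Monthly average = total cigarettes / 106 × 30.
- 18 cigarettes, all after V28: 18/106 × 30 = 5.1 per month, above the limit.
- 1 per day from V28 to V43: 38/106 × 30 = 10.8 per month.
- 15 per day from V28 to V43: 15 × 38 = 570; 570/106 × 30 = 161 per month, against 0 for V3 to V4, V3 to V14 and V3 to V28.

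**Step 4: do groups differ without any switching?** Yes. SAP 5.5.1 gives the case of 3 diary days out of 7: the subject falls into Others for Week 1 but can be analysed Overall. Such a subject would leave the Week 1 VO2max groups and stay in the V4 COHb table.

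**Step 5: is there any adjustment?** For the exposure markers, none: SAP 9.6.1.1.8 plans descriptive summaries only. The models for health markers, weight, body fat and waist include daily cigarette consumption (SAP 9.6.1.1.6 and 9.6.1.1.7), which lessens misgrouping without removing it. The step-count model (SAP 9.6.1.1.5) has only cigarette consumption at V1.

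**The case against.** The strongest reply is that one fixed grouping keeps the same subjects together across visits, that version 2.0 chose this simplification on purpose, and that the study tests no hypothesis (SAP 3.3.1). This stands as a reason to keep Overall for V43 and to ask for a modest change. It does not explain why V4 exposure markers should ignore a Week 1 category already derived for other V4 endpoints.

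Four stronger readings are tempting and are not supported:
- *V28 values are also grouped mostly by later use.* They are not; the later share is 36%.
- *The SAP says outright that all these values are grouped by Overall.* It speaks of the baseline, in the descriptive section, and SAP 5.5.1 allows group totals to fluctuate over time. The model sections name no classification period.
- *The V4 body-fat and waist model is certainly grouped by use up to V43.* SAP 9.6.1.1.7 points to Table 4, the V4 comparison table, and names no period. This is a gap, not a demonstrated misgrouping.
- *The link between product use, COHb and VO2max at one week is broken.* The VO2max model (SAP 9.6.1.1.1) considers each visit's COHb, and cigarette use from randomization to that visit, as candidate covariates at subject level. The relation can be examined there. What is lost is comparability between tables.

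Nor is this a plain breach of the protocol. Protocol 12.3 refers to categorising use within an analysis period, but leaves the detail to the SAP.

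**Conclusion.** The point holds for descriptive exposure markers at V4 and for exposure and health markers at V14, which on the coherent reading are grouped by a window that is 93% and 62% later than the measurement. It holds in part at V28 (36%). The V4 body-fat and waist model needs its period stated.

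This rests on the inference in Step 1 and on a full 106-day window. The second is realistic for compliant training-arm subjects, who must attend at least 34 of 38 sessions (SAP 8.3). For early terminations the window is shorter and the later share smaller. How many subjects would change group is unknown: the documents give no frequency of late switching, and the Figure 2 thresholds cannot be checked. In an exploratory study this is worth correcting because the main part costs almost nothing; it does not undermine the VO2max analysis.

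**What to change.** In SAP 9.6.1.2 and 9.6.1.1.7, state the classification period for each visit:
- V4: group all endpoints, including exposure markers, body fat and waist, by the Week 1 category already derived, with the matching acute baseline.
- V14 and V28: apply the Figure 2 rules to use from V3 to that visit, at least as a supportive table.
- V43: keep Overall.

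The later share of the classification window then falls from 93%, 62% and 36% to 0% at V4, V14 and V28, because each window ends at its visit.

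The V4 change needs no new derivation. For V14 and V28, SAP 5.5.2 and 5.5.3 already average cigarettes and HeatSticks from V3 to each visit; other nicotine products would need the same averaging. The costs:
- Group membership and baseline columns differ by visit, which SAP 5.5.1 already accepts.
- Subjects with more than 50% of the Week 1 diary missing fall into Others at V4. SAP 9.4 only lists Others, while SAP 9.6.1.2 gives them a descriptive column; that should be settled at the same time.
- A cumulative average still carries early cigarette use into later visits, so the fix removes grouping by future use but not all mixing of exposures.
- SAP 9.1.3.1 starts Month 1 at V5, so monthly summaries need a note that classification starts at V3.
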